4.2 STUDY POPULATION

4.2.1 SAMPLE SIZE CALCULATION

A minimum sample of 20 DE participants are required to complete the study and thus 25 DE participants will be enrolled. The standard deviation used to determine the sample size was derived from a previous study involving a comparison of fitting scleral contact lenses of different vaults in keratoconus patients and from evaluation of cornea thickness in controls and those having keratoconus (a plausible comparative group).

Power (i.e. the probability of correctly rejecting the null hypothesis) required for this study/experiment is 90% and type-I error is set to 0.05.

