2 PURPOSE AND HYPOTHESIS

The purpose of this study is to investigate the effects of scleral contact lens wear on a DE population using coated (Hydra-PEG) and uncoated (control) lenses. Symptoms of DE, quality of the tear film, quality of life, epithelial and overall corneal thickness, vision and comfort will be assessed before and after dispensing and wearing the lenses for four weeks.

The hypothesis is that **coated scleral contact lens wear is associated with improved ocular surface health in patients with dry eye disease (DED)**.

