3 OBJECTIVES

The specific objectives are:

1. To evaluate the impact of coated and non-coated scleral contact lenses on DE symptoms.
2. To assess the impact of the lenses on ocular surface health.
3. To measure the comfort and quality of life ratings of each lens type.
4. To determine the subjective ratings of each pair of lenses.

The primary outcome variables are:

1. Epithelial and corneal thickness
2. Quality of the tear film (osmolarity)
3. Levels of protease (inflammatory markers)
4. Contact Lens Impact on Quality of Life (CLIQ) questionnaire score
5. Contact Lens Questionnaire-8 (CLDEQ-8) questionnaire score

Other variables of interest:

- Hours of wear
- Subjective ratings of comfort, dryness, vision and burning.

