9 STATISTICAL ANALYSIS AND DATA MANAGEMENT

9.1 STATISTICAL ANALYSIS

All data described above will be analysed at the University of Waterloo from the eyes wearing the scleral lenses. Data analysis will be conducted using Statistica 13. Descriptive statistics will be used to analyse the baseline variables (age, gender, sagittal depth distribution, etc.). Table 3 lists the primary outcome variables and anticipated statistical procedures.

Table 3: Statistical procedures

| Variable | Analysis | Statistical test |
|---|---|------------------------------------|
| Parametric: tear clearance, corneal thickness, epithelial thickness, curvature, vision, osmolarity, comfort ratings | Comparison of lenses 1, 2 Comparison of epithelial and corneal thickness evaluation, osmolarity measurements | Paired t-test ANOVA RM-ANOVA |
| Nonparametric: OSDI, SPEED, CLDEQ-8, levels of protease | Comparison of ocular symptoms, quality of life, dryness, subjective assessment | T-test Mann-Whitney U test |

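### Five unranked primary outcomes (six measures) share one 0.05 and one 90% that are assigned to no outcome, with no multiplicity or success rule, and Table 3's primary list does not match section 3

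*Combined protocol and SAP*

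**What the plan says.** Section 2 gives one hypothesis, that "coated scleral contact lens wear is associated with improved ocular surface health in patients with dry eye disease (DED"). It names no outcome and no rule for what would support it.

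Section 3, under "The primary outcome variables are", numbers five items without ranking them: epithelial and corneal thickness, osmolarity, protease, CLIQ and CLDEQ-8. The first item holds two measures, so there are six.

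Section 4.2.1 asks for 20 completers (25 enrolled) and says that power "required for this study/experiment is 90% and type-I error is set to 0.05". It gives no outcome, target difference, SD value or sidedness. The SD comes from two sources. One is a comparison of scleral lens vaults, with no variable named. The other is described as "from evaluation of cornea thickness in controls and those having keratoconus".

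Section 9.1 says "Table 3 lists the primary outcome variables and anticipated statistical procedures". The table's variable cells read "Parametric: tear clearance, corneal thickness, epithelial thickness, curvature, vision, osmolarity, comfort ratings" and "Nonparametric: OSDI, SPEED, CLDEQ-8, levels of protease". The second row's analysis is "Comparison of ocular symptoms, quality of life, dryness, subjective assessment", and its tests are a t-test and the Mann-Whitney U test. Section 9.1 contains no alpha adjustment, ordering or success rule, and neither does any other section.

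**The concern.** With one hypothesis and six candidate measures, the reader needs to know which result, or how many, would support it. The three natural readings have different consequences:

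- **Any one significant primary is enough.** The chance of a false claim is well above the stated 5%.
- **All must be significant.** The error rate is controlled, but 90% power per test does not give 90% for the study.
- **Each outcome is its own claim.** Then 0.05 is a per-test rate and the 90% needs an owner. Section 4.2.1 says neither.

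With 20 completers, the result that counts as support could be chosen after the data are seen, and that cannot be repaired after unmasking. The mismatch between section 3 and Table 3 widens the choice.

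**Working it through.** **1. The plan's own figure.** The 20 completers cannot be reproduced, because the outcome, SD, difference, sidedness and test are not given. It can only be back-solved. For a paired t-test (noncentral t, 19 df, n = 20, alpha 0.05, power 0.90), the standardised paired difference is 0.76 two-sided or 0.68 one-sided. This is not the plan's stated target. Enrolling 25 fits an unstated 20% dropout: 20 / 0.80 = 25.

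**2. Any-one-wins error, each test at 0.05.** For independent tests the formula is 1 − 0.95^k. For equally correlated measures it was simulated (n = 20, paired t, two-sided; the correlations are assumptions).

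| Tests counted | Independent | Corr. 0.3 | Corr. 0.5 | Corr. 0.8 |
|---|---|---|---|---|
| 4 (two thicknesses, osmolarity, protease) | 1 − 0.95^4 = 18.5% | about 18% | about 16% | about 12% |
| 5 (section 3 items) | 1 − 0.95^5 = 22.6% | about 21% | about 19% | about 13% |
| 6 (section 3 measures) | 1 − 0.95^6 = 26.5% | about 24% | about 21% | about 14% |

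**3. The same with Table 3's unpaired test.** Mann-Whitney applied to crossover data ignores the pairing and is conservative. Simulated at n = 20, its true error is about 2.2%, 0.7% and 0.1% at assumed within-person correlations of 0.3, 0.5 and 0.7. With the six outcomes independent of each other:

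- CLDEQ-8 and protease by Mann-Whitney: 1 − 0.95^4 × 0.978^2 = 22%; 1 − 0.95^4 × 0.993^2 = 20%; 1 − 0.95^4 × 0.999^2 = 19%.
- CLIQ as well: 1 − 0.95^3 × 0.978^3 = 20%; 1 − 0.95^3 × 0.993^3 = 16%; 1 − 0.95^3 × 0.999^3 = 15%.

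So 26.5% becomes about 15% to 22%.

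**4. All-must-succeed power, 90% each.** Independent: 0.9^6 = 53%. Simulated at correlation 0.8: about 77%.

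**5. Cost of Holm.** If the 90% at n = 20 is for a two-sided paired t-test (difference 0.76) and only one of six effects is real, Holm power for that outcome is close to the power at 0.05/6 = 0.0083, which is about 68%. If all six effects are real, it is about 83% per outcome (independent) to 78% (correlation 0.8).

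**6. Table 3 against section 3.** Table 3 names 11 variables.

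- *In both:* corneal thickness, epithelial thickness, osmolarity, CLDEQ-8 and protease, which is five of the six measures.
- *Not named in Table 3:* CLIQ.
- *Added in Table 3:* tear clearance, curvature, vision, comfort ratings, OSDI and SPEED. Section 3 puts subjective comfort and vision ratings among the other variables.
- OSDI and SPEED are scheduled only at screening (sections 4.3.11 and 4.5.1, Table 2), before either lens is dispensed, so they cannot compare lenses.

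**7. Choices left open within the primaries.**

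- Corneal thickness is measured with both Spectralis and Pentacam (section 4.5.1). At follow-up it is imaged both on-lens and after removal (section 4.5.3).
- CLIQ is completed four times per lens (Table 2).
- CLDEQ-8 is completed twice per lens in Table 2, but weekly and at the end of each visit in section 4.3.11.
- Protease is InflammaDry MMP-9 in section 4.3.7 and Table 2, while sections 4.3.8 and 4.5.3 also assay tears from the lens bowl.

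**The case against.** **This is a small student-thesis study of commercially available lenses (sections 4.3.9 and 15).** That bears on severity. But the protocol states a hypothesis, labels outcomes primary and claims 90% power at 0.05. A study meant as exploratory would drop those claims.

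**Section 3 has separate objectives for symptoms, ocular surface health, and comfort and quality of life.** This stands in part. CLDEQ-8 and CLIQ fit objectives other than the section 2 hypothesis, so the four-measure range (18.5% to about 12%) answers that hypothesis most directly. It is still more than twice 5%.

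**Corneal thickness is plainly the powered outcome.** A reader might infer this from one of the two SD sources, but the text does not say it. If it is true, one sentence settles the matter.

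**The paired-test figures are not the tests in Table 3.** This is right for the second row if Mann-Whitney is used, and step 3 lowers the upper figure. The error remains well above 5%.

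**CLIQ has only a labelling gap.** This also stands. A reader might infer that CLIQ has been dropped from the analysis, but it is the protocol's only quality-of-life questionnaire and Table 3 does compare quality of life.

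**Section 4.4.2's reference to other primary outcome variables.** A reader might take this to mean CLIQ and CLDEQ-8 alone. Its example is not exhaustive, and Table 2 also schedules osmolarity and MMP-9 at follow-up.

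**Conclusion.** The point holds. The single 0.05 and single 90% belong to no named outcome, and no rule makes them true across six measures. Under an any-one-wins reading with paired tests, the error is 26.5% (independent) to about 14% (correlation 0.8) for six measures, and 18.5% to about 12% for the four ocular-surface measures. With Mann-Whitney where Table 3 may apply it, the independent six-measure figure is about 15% to 22%. Under an all-must-succeed reading, joint power is about 53% to 77%. These figures assume 20 completers, one value per participant, two-sided 0.05 and the stated correlations.

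Two stronger readings are not supported. The plan does not adopt an any-one-wins rule, so 26.5% is not its actual error rate; it neither states nor excludes that rule. Nor can it be said that 20 completers are too few, because the inputs needed to check this are not given.

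The open instrument and timepoint choices would be missing detail on their own; they matter here because they widen an unranked primary set. This should be fixed, and a rating below mandatory is defensible for a study of this kind.

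**What to change.** Before unmasking, adopt one of the following.

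**(a) One primary.** Name the outcome for which the sample size was actually calculated:

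> The primary outcome is [outcome sized], measured by [instrument], compared between lenses at visits 1-2 and 2-2 with a paired (crossover) test at two-sided 0.05. The 90% power applies to this outcome only, using SD [value used] and target difference [value used]. All other outcomes are secondary and no power is claimed for them.

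If the sponsor prefers a different primary, remove the 90% or restate the power at 20 completers from an SD for that outcome.

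**(b) Six measures with Holm:**

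> The six measures in section 3 are each compared between lenses with a paired test (Wilcoxon signed-rank or another paired method where nonparametric), using Holm at family-wise two-sided 0.05. The favourable direction for each is [state]. The hypothesis is supported only by Holm-significant results in that direction among epithelial thickness, corneal thickness, osmolarity and protease. CLIQ and CLDEQ-8 are reported as separate quality-of-life and symptom claims.

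Replace the blanket 90% with the power under Holm for the outcome sized (about 68% under the assumptions of step 5 if only one effect is real).

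**In either case:**

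- In Table 3, name CLIQ, label the added variables secondary, and remove OSDI and SPEED from the lens comparison.
- For each measure that stays primary, fix one instrument or assay and one timepoint. For thickness, also fix whether the on-lens or post-removal reading is used.
- Leave the section 4.4.2 sentence as it is, or list every remaining primary, including osmolarity and MMP-9.

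**Cost:** wording in sections 3, 4.2.1 and 9.1. No extra participants are needed under (a) if the primary is the outcome sized, or under (b) with the lower power disclosed. The downside is that fewer outcomes can be claimed at nominal 0.05, and the 90% covers at most one.

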4.2.2 NUMBER OF PARTICIPANTS

Recruitment: Participants who are patients of the University of Waterloo (UW) contact lens or ocular health clinics and those who are not UW patients but have previously participated in DE studies through CORE will be invited to participate in this study. With the patient's permission, the investigators will initiate recruitment according to the in-person script or flyers approved by the Office of Research Ethics (Appendices 1a-c). The investigators will discuss the project where any questions regarding the study procedures and any risks associated with the study can be answered. Eligibility will be determined using the inclusion and exclusion criteria. Current contact

lens wear of any lens type is not necessary for the DE participants. Informed consent will be obtained for all participants prior to their enrollment in the study (Appendix 2).

INCLUSION CRITERIA

A person is eligible for inclusion in the study if he/she:

- Is at least 18 years of age and has full legal capacity to volunteer.
- Has read, understood, and signed the information consent letter.
- Has been diagnosed with dry eyes.
- Has reduced tear break up time (NITBUT) and/or reduced tear meniscus height (TMH), clinical sign of dry eye disease and contact lens discomfort or is symptomatic of dry eye.
- Is willing and able to follow instructions and maintain the appointment schedule.
- Has greater than 13 points on the OSDI.
- Has greater than 4 points on the Standardized Patient Evaluation of Eye Dryness (SPEED).

EXCLUSION CRITERIA

A person will be excluded from the study if he/she:

- Is using any topical medications that will likely affect the study outcome.
- Has undergone any form of corneal surgery.
- Has any known allergies or sensitivity to the diagnostic pharmaceuticals or products, such as fluorescein, used in this study.
- Has persistent, clinically significant corneal or conjunctival staining using sodium fluorescein dye not related to the signs of dry eye.
- Has any clinically significant lid or conjunctival abnormalities and active neovascularization on the cornea.
- Anatomic variations of the conjunctiva that can impair proper scleral or soft contact lens wear/fitting
- Ocular pathology other than dry eye (e.g. glaucoma, macular degeneration) which may significantly impact visual function and assessment.
- Is participating in any other type of eye related clinical or research study.
- Has any active ocular infection and may require topical medications.
- Currently taking any systemic medication that may affect the study outcome.
- Is pregnant
- Has been diagnosed, recovered, or tested positive but asymptomatic with COVID-19.

For the purposes of this study, active ocular disease is defined as infection or inflammation which requires therapeutic treatment. Mild (i.e. not considered clinically relevant) lid abnormalities (blepharitis, meibomian gland dysfunction, papillae), corneal and conjunctival staining and dry eye are not considered active ocular disease. Neovascularisation (non-active) and corneal scars are the result of previous hypoxia, infection or inflammation and are therefore not considered as active ocular disease.

4.3 STUDY MATERIALS

4.3.1 SLIT LAMP BIOMICROSCOPE WITH CAMERA

The slit lamp biomicroscope with mounted high-speed camera, a standard optometric class II medical device, commercially available in Canada (Health Canada licence #69113), will be used to assess the ocular surface and the adnexa during the screening process, contact lens fitting and assessment of the cornea following the contact lens wear.

4.3.2 OCULUS PENTACAM

The Oculus Pentacam HR®, a standard optometric class II medical device which is commercially available in Canada (Health Canada licence #69466) will be used for the measure of corneal curvature and thickness.

4.3.3 KERATOGRAPH 5M

The Oculus Keratograph® 5M, a standard optometric class II medical device which is commercially available in Canada (Health Canada licence #90001) will be used for imaging the corneal surface with fluorescein.

4.3.4 VISANTE OCT

The Visante OCT (Optical Coherence Tomographer), a standard optometric class II medical device, commercially available in Canada (Health Canada licence #69113), will be used to measure the sagittal height of the eye to assist with scleral contact lens fitting.

4.3.5 SPECTRALIS OCT

The Spectralis OCT, a standard optometric class II medical device commercially available in Canada (Health Canada license #76040), will be used to measure the epithelial and corneal thickness before and after scleral contact lens wear. It will also be used to measure the corneal clearance when the lens is initially applied and then after four weeks, for each of the scleral lens designs.

4.3.6 TEARLAB OSMOLARITY SYSTEM

Tearlab Osmolarity System (TearLab Corp. Escondido, CA, USA), a medical device class III which is commercially available in Canada (Health Canada licence #81402) will be used to detect and indirectly measure the levels of osmolarity of the tear film.

4.3.7 INFLAMMADRY® TEST KITS

InflammaDry® (RPS InflammaDry, Sarasota, Florida, USA) is a hand-held, point-of-care diagnostic device (for immunoassay measurements) which is commercially available in Canada and licensed under Labtician Ophthalmics, Inc. (Health Canada licence # 86888). It will be used to detect the levels of protease (MMP-9) in the tear film.

4.3.8 TEAR FILM ANALYSIS

Analysis of the tear film in the scleral lens bowl only will be performed using Meso Scale Discovery system (MSD-ECL). Tears collected at the screening visit (from the ocular surface) will be used as a baseline. After tear collection, the tear samples will be stored at -80°C until analysis. The tears will be assayed for matrix metalloproteinases and cytokines using commercially available MSD kits. Preparation and analysis of samples will be followed as per instructions supplied by the manufacturer. The tear collection process is detailed in Appendix 19 (SOP for Capillary Tear Film Collection from the Bowl of the Scleral Lens).

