4.3.10 CONTACT LENS CARE SYSTEM AND ASSESSMENT

The lens care systems that will be used by the investigator/participants during the trial fitting and the dispensing of the scleral contact lens in this study are: Clear Care Disinfecting Solution (Health Canada license #02245661), Boston Simplus Comfort Formula Conditioning solution (Health Canada license #02019868), Sensitive Eyes Saline Plus (Health Canada license #6208410) and Minims Saline (Health Canada license #02148501) (Bausch + Lomb, Rochester, NY, USA). Clear Care and Disinfecting Solution will be used to disinfect the scleral contact lens overnight (minimum of 6 hours) of disinfection. Boston Simplus Comfort Formula Conditioning solution will be used to provide lubrication (initial comfort) on the front surface of the lens before lens application and also to store the lens when not in use. The lenses will be rinsed thoroughly with Sensitive Eyes Saline Plus and filled with Minims Saline before insertion. Sodium fluorescein strips (Health Canada license #02179539) (Fluorets; Laboratoire Chauvin, Aubenas, France) will be used during the trial fitting of the scleral contact lenses.

Participants will be carefully instructed following the manufacturers' recommendation for caring for the lenses before dispensing.

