4.4.2 STUDY VISITS

This study will involve 5 visits over 5 study days in total. The total time commitment for all study visits is approximately 9 hours spread over a 3-month period (See Table 1). The total study visit time commitment may be different for each participant, as the needed visit time will depend on how easily the lenses can be fitted.

The first visit will involve screening and baseline measurements of the participants. The investigator will determine the eligibility of the participant using the inclusion/ exclusion criteria, questionnaires, and tear film analysis (osmolarity and protease levels). Ineligible participants will be discontinued from the study. Eligible participants will be trial fit with the most appropriate scleral lenses (Visit 0-0) as determined by the baseline measurements obtained at the screening visit/appointment. Tear collection from the ocular surface will also be performed as a baseline for comparison with collection from the scleral bowl in the dispensing and follow up visits with the scleral lenses. Participants will be instructed on insertion/application, removal, and proper handling and care of the lenses before dispensing the contact lenses (Visit 1-1, 2-1). Participants will be instructed on insertion, removal, and proper handling and care of the lenses before dispensing the contact lenses (Visit 1-1, 2-1). At each of the lens dispensing/delivery appointments, the researcher will dispense/deliver the study lenses and supplies (contact lens care system). Measurements including visual acuity, topographic corneal clearance, fluorescein assessment will be obtained while the participant is wearing the lenses. The tear collection (from the scleral lens bowl) will be collected immediately the lens is removed from the eye. Study questionnaires (CLDEQ-8, CLIQ and wearing habit/experience log along with the subjective grading scales) will also be handed out to the participants. These questionnaires will be filled each week and biweekly for each of the scleral lens pair for the four weeks wearing schedule.

After the participant has worn the lenses for 8 to10 hours during the day (2 pairs: uncoated scleral contact lens or Hydra-PEG coated scleral contact lens, randomly selected), the participant will return for a follow up visit four weeks later for each pair.

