4.5.3 FOLLOW-UP VISIT

Following the four weeks of the contact lens wear, the participant will present at the follow-up visit (visits 1-2, 2-2). The lens will be examined with the slit lamp biomicroscope. This will be

followed by visual acuity and imaging with Spectralis OCT (to assess corneal clearance and cornea thickness).

The investigator will carefully remove the contact lens from the eye and immediately collect the tears from the lens bowl for tear analysis. Levels of protease and cytokines in the tears will be assessed.

Slit lamp biomicroscopy mounted camera will be used to assess the corneal integrity and staining. This will be followed by imaging with the Keratograph 5M (for staining) and Spectralis OCT for corneal thickness measurements.

The questionnaire administered (CLDEQ-8, CLIQ and wearing habit/experience along with subjective grading scales) will be collected and reviewed for completeness.

The above-described procedures will be followed for all the lenses to be used in the study.

Table 2 lists a summary of procedures to be conducted at scheduled visits.

Table 2: Summary of procedures at scheduled visits

| Visit | Procedure | Instrument/ application | Form (Appendix #) |
|---|---|---|---|
| Screening, Baseline visit and Trial Lens Fitting (Visit 0-0) | Informed Consent | - | ICL (2) |
| | Demographics & Med. History | - | Screening Form (3) |
| | Ocular surface disease | Self-Administered Questionnaire | OSDI questionnaire (4) |
| | Evaluation of Eye Dryness | Self-Administered Questionnaire | SPEED questionnaire (5) |
| | Vision assessment | LogMAR chart | Study Visit Form for Scleral Lenses (6) |
| | Osmolarity | Tearlab osmolarity system | Study Visit Form for Scleral Lenses (6) |
| | Level of protease (MMP-9) | InflammaDry | Study Visit Form for Scleral Lenses (6) |
| | Tears from ocular surface | Micropipette tear collection kit | Study Visit Form for Scleral Lenses (6) |
| | Ocular surface imaging | Keratograph 5M (K5M) | Study Visit Form for Scleral Lenses (6) |
| | Sagittal height/corneal topography | Visante, Spectralis and Pentacam | Study Visit Form for Scleral Lenses (6) |
| | Biomicroscopy | Slit-lamp with camera | Biomicroscopy Form (7) |
| | Auto-refraction | Auto-refractor | Study Visit Form for Scleral Lenses (6) |
| TRIAL LENS FITTING | | | |
| Lens fitting and examination | Slit lamp with camera | Study Visit Form for Scleral Lenses (6) | |

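### MSD tear markers take ocular-surface tears as baseline for saline-filled lens-bowl fluid; Table 3 lists OSDI and SPEED, measured once, and unpaired tests for crossover data

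*Combined protocol and SAP*

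**What the plan says.** **Tear markers.** Section 4.3.8 describes the MSD assay of matrix metalloproteinases and cytokines: "Analysis of the tear film in the scleral lens bowl only will be performed". It then adds: "Tears collected at the screening visit (from the ocular surface) will be used as a baseline". Section 4.4.2 confirms the intended use, with the surface collection serving "as a baseline for comparison with collection from the scleral bowl in the dispensing and follow up visits". Under section 4.3.10 the lenses are rinsed and "filled with Minims Saline before insertion".

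**Protease outcome.** Section 3 makes protease levels one of five primary outcomes. On the InflammaDry kit, section 4.3.7 says: "It will be used to detect the levels of protease (MMP-9) in the tear film". Section 4.4.1 and the screening rows of Table 2 also link protease to that kit. Section 4.5.3, directly after describing collection from the bowl, says: "Levels of protease and cytokines in the tears will be assessed".

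**Symptoms and tests.** Section 2 sets up a study of "coated (Hydra-PEG) and uncoated (control) lenses" and says that dry eye symptoms, among other measures, "will be assessed before and after dispensing and wearing the lenses for four weeks". Section 4.3.11 and Table 2 place OSDI and SPEED at recruitment and screening. The follow-up rows of Table 2 list only CLDEQ-8, CLIQ and the wearing log. Table 3 (section 9.1) nevertheless puts OSDI and SPEED with CLDEQ-8 and protease in a row whose analysis is a comparison. The tests listed for that row are a t-test and the Mann-Whitney U test. The parametric row does name a paired t-test.

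**The concern.** Three things in the plan do not fit together.

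1. The MSD baseline and the on-lens sample differ in site, and one of them starts as saline. A marker could appear to fall only because it is diluted, or to rise because it accumulates under the lens. Either could be read as a change in ocular surface inflammation.
2. A comparison of OSDI or SPEED needs at least two values per person, and the schedule gives one.
3. Each participant wears both lenses, so the two values are correlated. A test that treats them as independent samples discards the advantage of the crossover. Table 3 also numbers the lenses 1 and 2, the labels that Table 1 uses for order of delivery. That leaves coated against uncoated unstated in the table.

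**Working it through.** **Step 1: the plan's own figure.** Section 4.2.1 gives 20 completers, 90% power and a type I error of 0.05, but neither an SD nor an effect size, so 20 cannot be reproduced. It can be inverted. For a two-sided paired t-test with 19 degrees of freedom, 90% power at n = 20 needs a difference of 0.764 SD of the within-person difference. The normal approximation gives (1.960 + 1.282)/√20 = 0.725.

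**Step 2: surface against bowl, no lens effect.** Let the bowl concentration be f times the surface concentration, where f is the tear fraction of the sample. The mean log difference is then ln f, and the paired t-test has noncentrality |ln f| × √20 / SD. The documents give neither f nor the SD, so both are assumed.

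| Saline share | ln f | False fall, SD 0.3 | SD 0.5 | SD 1.0 |
|---|---|---|---|---|
| 10% | −0.105 | 32% | 14% | 6.5% |
| 20% | −0.223 | 88% | 47% | 16% |
| 50% | −0.693 | 100% | 100% | 84% |

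For the 20% row the noncentralities are 0.223 × 4.472 / SD = 3.33, 2.00 and 1.00. If the marker also accumulates under the lens by a factor g, the mean becomes ln(f × g). This is positive once g exceeds 1/f, which is 1.25 at 20% saline. The net direction is therefore unknown.

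**Step 3: bowl against bowl.** The mean log difference is the lens effect plus ln(f coated / f uncoated). The second term averages zero only if f does not depend on the coating. Assume that f varies uniformly from 0.2 to 0.9, independently at each visit.

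- *False positives, no lens effect:* about 5% for all three SDs. Surface against bowl with the same inputs gives false falls in 100%, 99.5% and 75% of trials.
- *Loss of power:* the variance of ln f is 0.6254 − 0.6756² = 0.169, so dilution adds an SD of √(2 × 0.169) = 0.58 to the difference. The total SD is √(0.3² + 0.58²) = 0.65, and likewise 0.77 and 1.16. An effect with nominal 90% power keeps about 32%, 56% or 80%.
- *Coating-dependent dilution:* if the tear fraction is 20% higher under one lens (ln 1.2 = 0.182), false positives rise to about 22%, 17% and 10%.

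**Step 4: unpaired test on paired data.** With equal SDs and within-person correlation r, the SD of the difference is SD × √(2(1 − r)). Take the effect from step 1, 0.764 of that quantity. By simulation at n = 20, Mann-Whitney has about 81%, 67% or 40% power at r = 0.3, 0.5 or 0.7 (assumed values). The Wilcoxon signed-rank test keeps 88–89%.

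**Step 5: OSDI and SPEED.** They are scheduled at 1 of 5 visits and at 0 of the 2 follow-up visits. Neither a change nor a between-lens difference can be calculated.

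**The case against.** **Primary outcome.** A reader might infer that the baseline mismatch undermines the primary protease outcome. The documents do not support that. Sections 4.3.7 and 4.4.1 and Table 2 mostly tie protease to InflammaDry, which is scheduled at screening and at follow-up. MSD may be only a supplementary assay. Some ambiguity remains, because section 3 does not name the assay and section 4.5.3 speaks of protease just after the bowl collection.

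**Dilution correction.** Appendix 19, the collection procedure, was not supplied, so it cannot be said that no correction exists, only that none appears in the supplied text. A dilution correction would still leave the difference in sampling site.

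**Same-fluid reference.** Section 4.4.2 and Table 2 also list bowl samples at delivery. The plan does not name these as the baseline, and it does not state the interval from insertion to sampling.

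**The between-lens contrast.** It is tempting to say that coated against uncoated escapes the problem. Step 3 shows that this is too strong: it is unbiased only under a condition on which the documents are silent, and it loses power if dilution varies.

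**Table 3.** It lists anticipated procedures, and its layout may have suffered in text extraction. The lens numbers could well mean coated and uncoated, since section 2 names the uncoated lens as control. A reader might also conclude that CLIQ is left out of the analysis. It is missing from the variable list, but the analysis cell mentions quality of life. These points call for clearer wording and do not show that a wrong analysis is intended.

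**The word only in section 4.3.8.** It need not contradict the surface baseline. It can simply restrict sampling during lens wear to the bowl.

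**Conclusion.** The concern holds in three limited parts.

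- Change from screening in MSD markers cannot be read as a lens effect. The size and direction of the distortion are unknown, and the percentages in step 2 illustrate assumed saline shares and SDs; they do not estimate what will happen in this trial.
- The OSDI and SPEED comparison in Table 3 cannot be carried out on the stated schedule. This rests on the documents alone.
- The tests named for CLDEQ-8 and protease are not stated as paired. If Mann-Whitney were used, an effect with 90% power under a paired t-test would have about 81% to 40% power over the assumed correlations of 0.3 to 0.7.

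This should be fixed before analysis. It does not show that the primary protease outcome or the between-lens comparison is invalid.

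**What to change.** 1. **Sections 4.3.8 and 4.4.2.** Test MSD markers bowl against bowl, coated minus uncoated within participant, at Visits 1-2 and 2-2. Report the surface sample descriptively and stop using it as the baseline for bowl values. State that the contrast is unbiased only if the saline share does not depend on the coating, and that variable dilution lowers its power.
2. **Table 3.** Replace Mann-Whitney with a paired test such as Wilcoxon signed-rank, label the lenses coated and uncoated, and add CLIQ to the variable list.
3. **OSDI and SPEED.** Either give both at Visits 1-2 and 2-2, or remove them from the comparison row of Table 3.

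**Cost.** Items 1 and 2 are wording changes, because the follow-up bowl samples are already scheduled. Item 3 adds two short questionnaires at two existing visits if the first option is taken. The downside is that the trial gives up any confirmatory MSD claim of change from the no-lens state.
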